6.3.2 Dose modification and dose interruption for spartalizumab and siltuximab

General dose modification instructions:

Siltuximab and spartalizumab have class-specific safety profiles based on their mechanism of action but may also cause AEs that overlap. For management of AEs which can be clearly attributed to siltuximab or spartalizumab, independent dose modification for either agent is allowed. For AEs without clear attribution to either study treatment, management of toxicity should include dose modifications of both agents.

Overall AEs are to be graded according to NCI-CTCAE v4.03 (http://ctep.cancer.gov). All dose interruptions and the reason for the dose interruption must be documented in the eCRF.

Overall, patients with AEs suspected to be related to *spartalizumab* including those of potential immune-mediated etiology (irAE) may need to interrupt or permanently discontinue spartalizumab as outlined in Section 6.3.2. In general, study treatment with spartalizumab must be permanently discontinued in case of:

- Any life-threatening adverse reactions (excluding endocrinopathies controlled with hormone replacement therapy)
- Persistent Grade 2 or 3 adverse reactions (excluding endocrinopathies controlled with hormone replacement therapy) that do not recover to <= Grade 1 within 12 weeks after last dose of study treatment
- Inability to reduce the dose of steroids (for the management of irAE) to 10 mg/day or less of prednisone or equivalent (or as indicated in the tables below) within 12 weeks
- Any severe or Grade 3 recurring treatment-related adverse reaction

The 12 weeks' timeframe will begin from the time the irAE reaches a grade that leads to spartalizumab interruption.

Overall, patients with AEs suspected to be related to *siltuximab* include pruritus, increased weight (edema), rash, hyperuricemia, neutropenia, and upper respiratory tract infection. Rare side effects include gastrointestinal perforation. Toxicities may require interruption of therapy,

Protocol/Version No.: 5, Date December 15, 2022

dose reduction or permanent discontinuation from trial as detailed in section 6.3 and Tables 8-8 and 8-9. In general study treatment with siltuximab must be discontinued for:

- Gastrointestinal perforation
- Grade 4 weight gain
- Grade 4 upper respiratory tract infection
- Recurrent or severe grade 3 treatment-related adverse events.
- Life threatening adverse events
- Interruption of therapy for longer than 12 weeks

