other clinical sequelae (e.g., renal impairment, pulmonary infiltrates) Grade 4: Life-threatening; pressor or ventilatory support indicated	 Acetaminophen Narcotics Oxygen Pressors Corticosteroids Epinephrine Increase monitoring of vital signs as medically indicated until the patient is deemed medically stable in the opinion of the investigator. Hospitalization may be indicated. 	

2nd occurrence of grade 2 irAE (including colitis/diarrhea, LFT abnormalities, rash, nephritis and other AEs as listed in table 8-6) or for grade 2 irAE lasting more than 12 weeks. Permanently discontinue spartalizumab.

6.3.2.1.2 Guidance for corticosteroids tapering for management of immune-related AEs:

Steroids should be tapered slowly and based on response/recovery of clinical symptoms. Consider to complete tapering over a period of at least 4 weeks. Slower tapering of corticosteroids therapy may be recommended if the adverse event is not showing improvement.

Protocol/Version No.: 5, Date December 15, 2022

Once corticosteroid tapering is achieved at a level of 10 mg of prednisone/day (or equivalent), spartalizumab can be restarted as indicated in the dose modification tables.

6.3.2.2 Dose modification requirements for adverse events suspected to be related to study treatment

The required dose modification and management of adverse events that are considered to be related to study medication and do not have specific management requirements noted elsewhere in the protocol are provided in Table 8-8 & Table 8-9.

Table 8-8 Mandatory dose modification requirements and recommended clinical management guidelines for hematologic adverse events suspected to study treatment

Hematologic su	spected AEs (NCI-CTCAE v4.03)	
Grade	Recommended Adverse Event management guidelines	Mandatory Dose Modification requirements
Neutropenia		
Grades 1, 2	NA	Continue spartalizumab and siltuximab

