Grade 3, 4	Monitoring blood test more frequently (every 7 days for grade 3, and 3-5 days for grade 4) Consider consulting with a specialist, initiation of corticosteroids or other therapies as medically appropriate and as per institutional guidelines.	1st occurrence: Interrupt spartalizumab and siltuximab until toxicity recovers to Grade ≤2 or baseline. Once recovered restart spartalizumab and siltuximab treatment at the same dose and schedule Grade 4 febrile neutropenia or thrombocytopenia should lead to permanent discontinuation of spartalizumab and siltuximab 2nd occurrence: Interrupt spartalizumab and siltuximab until toxicity recovers to Grade ≤2 or baseline Once recovered restart spartalizumab and siltuximab treatment at the same dose and schedule
		AE resolution to ≤ Grade 2 or baseline must occur within a maximum period of 12 weeks since Grade 3 or 4 event has been identified, otherwise spartalizumab

Grade	Recommended Adverse Event management guidelines	Mandatory Dose Modification requirements
		and siltuximab must be permanently discontinued
		3 rd occurrence:
		Permanently discontinue spartalizumab and siltuximab
Febrile Neutropenia	Apply Institutional guidelines	Follow- neutropenia Grade 4 requirements (above)
Thrombocytopeni	ia (NCI-CTCAE v4.03)	
Grade 1, 2, 3 without clinical significant bleeding	Grade 3: monitoring blood test more frequently (every 7 days)	Continue spartalizumab and siltuximab
Grade 3 with	Monitoring blood test more frequently	1 st occurrence:
clinical significant bleeding OR Grade 4	(every 3-5 days) Consider consulting with a specialist, initiation of corticosteroids or other therapies as medically appropriate and as per institutional guidelines.	 Interrupt spartalizumab and siltuximab until toxicity resolves to Grade ≤2 or baseline. Once recovered restart spartalizumab and siltuximab at the same dose and schedule
		2 nd occurrence:
		 Interrupt spartalizumab and siltuximab until toxicity resolves to Grade ≤2 or baseline Once recovered restart spartalizumab and siltuximab at the same dose and schedule
		AE resolution to ≤ Grade 2 or baseline must occur within a maximum period of 12 weeks since Grade 3 with clinically significant bleeding or Grade 4 event has been identified, otherwise spartalizumab and siltuximab must be permanently discontinued.
		3 rd occurrence:
		permanently discontinue spartalizumab and siltuximab

Protocol/Version No.: 5, Date December 15, 2022

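### Table 8-8 gives two incompatible mandatory actions for a first Grade 4 thrombocytopenia that is neither immune-mediated nor life-threatening: stop both drugs permanently, or interrupt and restart both at the same dose

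*Combined protocol and SAP*

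**What the plan says.** The title of Table 8-8 is "Mandatory dose modification requirements and recommended clinical management guidelines for hematologic adverse events suspected to study treatment". Section 6.3.2.1.1 adds that the dose modification column binds, while the management advice may follow local practice. Section 6.3.2.2 sets the scope: requirements for related events that "do not have specific management requirements noted elsewhere in the protocol are provided in Table 8-8" and Table 8-9.

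Two entries in the mandatory column reach Grade 4 thrombocytopenia:

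- The neutropenia row for Grades 3 and 4, under the first occurrence: "Grade 4 febrile neutropenia or thrombocytopenia should lead to permanent discontinuation of spartalizumab and siltuximab".
- The thrombocytopenia row for Grade 3 with significant bleeding, or any Grade 4. At the first occurrence both drugs are interrupted until the toxicity falls to Grade 2 or below, or to baseline. Then: "Once recovered restart spartalizumab and siltuximab at the same dose and schedule". The second occurrence is handled in the same way. Permanent discontinuation follows at the third occurrence, or if there is no recovery within 12 weeks "since Grade 3 with clinically significant bleeding or Grade 4 event has been identified".

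Section 6.3.2 also lists general reasons to stop. For both drugs these include life-threatening events. For spartalizumab they include "Any severe or Grade 3 recurring treatment-related adverse reaction", and for siltuximab "Recurrent or severe grade 3 treatment-related adverse events". Section 6.3.2.1.1 stops spartalizumab for any Grade 4 immune-related event.

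**The concern.** A patient who recovers from a first Grade 4 thrombocytopenia cannot be both permanently stopped and restarted. Both instructions stand in a column that the protocol calls mandatory, so an investigator who follows one departs from the other, and two investigators could treat identical patients differently.

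The event is not trivial: Table 7 makes it dose-limiting when it occurs in the first 6 weeks. One row re-exposes the patient to both drugs without dose reduction. The other ends trial therapy for someone whose alternatives Section 5.4 describes as very limited.

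**Working it through.** The point is textual and the plan gives no figure to reproduce. The check sets the entries side by side, looks for a rule that decides between them, and then follows the consequences.

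**1. The two entries, for a first treatment-suspected Grade 4 thrombocytopenia that recovers within 12 weeks**

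| | Neutropenia row (Grades 3, 4) | Thrombocytopenia row (Grade 3 with bleeding, or Grade 4) |
|---|---|---|
| 1st occurrence | Stop both permanently | Interrupt, restart both at same dose |
| 2nd occurrence | Does not arise | Interrupt, restart both at same dose |
| 3rd occurrence | Does not arise | Stop both permanently |
| Same-dose restarts possible | 0 | up to 2 |

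The 12-week sentence in the thrombocytopenia row names Grade 4, so the restart rule plainly covers it.

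**2. Is there a rule of precedence?**

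- Immune-mediated Grade 4 event: Section 6.3.2.1.1 stops spartalizumab, and Section 6.3.2 then stops siltuximab by default, with stated exceptions. This is largely settled.
- Life-threatening event: Section 6.3.2 stops both. This is settled.
- Section 6.3.3, item 6, sends hematologic toxicity back to Section 6.3.2.2. It does not choose between rows.
- A first Grade 4 platelet count that is neither immune-mediated nor life-threatening: no text decides.

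**3. Can the stop sentence be read so that the conflict disappears?**

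- If Grade 4 qualifies only febrile neutropenia, thrombocytopenia of any grade would mean a permanent stop. That contradicts the row that continues both drugs for Grades 1 to 3 without significant bleeding.
- If it means only thrombocytopenia that accompanies Grade 3-4 neutropenia, the text does not say so. A patient with both would still get a stop from one row and a restart from the other.
- A cell displaced when the PDF was read would not explain it, because the sentence itself names thrombocytopenia.

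**4. Does it reach the design decisions?** Grade 4 thrombocytopenia is a criterion in Table 7 whichever row is followed. Under Section 6.2.2 a patient with such an event in the first 6 weeks is evaluable for escalation. The expansion stopping rule in Section 12.1 uses the same table. Escalation counts, the recommended phase 2 dose and that rule are therefore the same under either row. The summaries of events leading to discontinuation (Section 12.5.1.1) and of dose modifications (Section 12.5.1.3) can differ.

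**5. How many patients?** The only related counts are in Section 4.1.2.1, Table 3: Grade 3-4 thrombocytopenia, grades pooled, over the first 8 infusions in Castleman's disease.

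- Siltuximab: 2/53 = 3.8% (exact 95% CI 0.5% to 13.0%). Placebo: 1/26 = 3.8% (0.1% to 19.6%). Difference = 0.0377 - 0.0385 = -0.0007, so no observed excess.
- If 2/53 carried over (an assumption), the planned 27 to 42 treated patients would include 27 x 2/53 = 1.0 to 42 x 2/53 = 1.6 with any Grade 3-4 event. At the upper confidence limit the figure is 42 x 0.1298 = 5.5.

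The affected cases are an unknown subset: Grade 4 only, suspected related, not immune-mediated, not life-threatening, and recovered. The documents give no Grade 4 rate and no rate for the combination, so these figures give context and do not estimate the number affected.

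**The case against.** The strongest reply is that the undecided case is narrow and other safeguards exist. Section 5.4 lists cytopenias among possible immune-mediated events, and such cases have their own rule. Section 6.3.2 allows either drug to be modified alone when attribution is clear. The investigator may stop a drug thought detrimental (Section 6.7), unacceptable adverse experiences require discontinuation (Section 6.2.5), and the study team reviews all toxicity logs (Section 11.0). All of this stands and keeps the point small. None of it chooses between the two rows.

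It can also be said that the stop sentence uses *should* and not *must*. It still sits in the mandatory column, and the opposing row carries no discretion clause.

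A reader might go further in three ways that the documents do not support:

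- *That permanent stopping was clearly meant and the restart row is unsafe.* The protocol points both ways. It restarts after Grade 3-4 neutropenia, and Table 8-9 allows restart after a first Grade 4 non-hematologic event if benefit-risk favors it. Yet Section 6.3.3 stops siltuximab at a first Grade 4 weight gain, hyperuricemia or upper respiratory infection.
- *That the Section 6.3.2 recurrence rules limit the difference to a single restart.* Those rules are introduced as general, and for siltuximab the same section refers to Tables 8-8 and 8-9 for detail. Whether they override a second restart is a separate and less certain question. If their wording on severe reactions were read to compel stopping at the first event, the restart row would contradict them and would still need editing.
- *That dose-finding is compromised.* Step 4 of the working shows that it is not.

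**Conclusion.** The contradiction is real, but it is confined to one case: a first treatment-suspected Grade 4 thrombocytopenia, neither immune-mediated nor life-threatening, that recovers within 12 weeks. For that patient Table 8-8 requires either no re-exposure or up to two same-dose restarts, and no text decides.

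Few or no patients are likely to be affected. That judgment rests on the low pooled counts in Castleman's disease and on the narrowness of the case; the number itself cannot be estimated. The consequences are the management of that patient and small shifts in descriptive safety tables. The point is minor. It merits correction because it is a safety instruction that cannot be followed as written and is easily put right.

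**What to change.** Make Table 8-8 give one action, chosen by the clinical team from two options:

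- (a) Delete *or thrombocytopenia* from the neutropenia row, so that the thrombocytopenia row alone governs.
- (b) Give Grade 4 thrombocytopenia its own row requiring permanent discontinuation of both drugs, subject to the Section 6.3.2 allowance for modifying one agent when attribution is clear. Remove Grade 4 from the interrupt-and-restart row and from its 12-week sentence, and delete *or thrombocytopenia* from the neutropenia row.

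Neither option requires a change to the second-occurrence action. The cost is a wording edit to identified rows of one table in the next amendment, with no effect on sample size, design or analysis.

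### Table 8-8 gives two opposite mandatory actions for Grade 4 thrombocytopenia that is not immune-mediated

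*Combined protocol and SAP*

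**What the plan says.** Table 8-8 in Section 6.3.2.2 has a column of mandatory dose modifications for hematologic events suspected to be related to treatment. In the Grade 3 and 4 neutropenia row, within the first-occurrence instructions, that column states: "Grade 4 febrile neutropenia or thrombocytopenia should lead to permanent discontinuation of spartalizumab and siltuximab".

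The same table has its own thrombocytopenia row. Its grade cell includes "clinical significant bleeding OR Grade 4". The action at both the first and the second occurrence begins "Interrupt spartalizumab and siltuximab until toxicity resolves to Grade ≤2 or baseline", followed by restart of both drugs at the same dose and schedule. Permanent discontinuation comes at the third occurrence, or if the event has not resolved within 12 weeks.

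Section 6.3.2 also has general stop lists, each opened with the qualifier that they apply in general. The spartalizumab list includes "Any severe or Grade 3 recurring treatment-related adverse reaction" and the siltuximab list includes "Recurrent or severe grade 3 treatment-related adverse events". Both lists include life-threatening events. The siltuximab paragraph refers the reader onward for "dose reduction or permanent discontinuation from trial as detailed in section 6.3 and Tables 8-8 and 8-9". For Grade 3 or 4 neutropenia, Table 8-8 reads "2nd occurrence: Interrupt spartalizumab and siltuximab until toxicity recovers to Grade ≤2 or baseline Once recovered restart spartalizumab and siltuximab treatment". Table 8-9 likewise restarts both drugs after a second Grade 3 non-hematologic event. After a first Grade 4 event it asks the investigator to consider stopping spartalizumab permanently, but permits restart of both drugs if benefit-risk supports it.

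**The concern.** An investigator whose patient has a first Grade 4 platelet event finds two instructions in one mandatory column. One ends treatment with both drugs; the other resumes both at full dose after recovery. Following either breaches the other, so compliance cannot be judged. The clinical stakes run both ways: re-exposure at full dose after a Grade 4 cytopenia, or loss of therapy in a population that Section 5.4 describes as having few effective options.

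The general lists raise a second, weaker question: whether a recurrent Grade 3 or a life-threatening related event must end treatment, or may be followed by the restarts that Tables 8-8 and 8-9 allow.

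**Working it through.** There is no plan figure to reproduce, so the check sets the texts side by side.

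**Step 1. Grade 4 thrombocytopenia within Table 8-8.** If a rule stops treatment permanently at occurrence n, it allows n − 1 restarts.

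| Source in Table 8-8 | Permanent stop at | Restarts allowed |
|---|---|---|
| Sentence in the neutropenia row | 1st occurrence (n = 1) | 1 − 1 = 0 |
| Thrombocytopenia row | 3rd occurrence (n = 3) | 3 − 1 = 2, if each event recovers within 12 weeks |

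The sentence names thrombocytopenia, so the conflict does not depend on how the table was laid out.

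**Step 2. Other readings of the sentence.** If the Grade 4 qualifier attached only to febrile neutropenia, thrombocytopenia of any grade would end treatment. That widens the conflict, because the table continues both drugs for Grades 1 to 3 without clinically significant bleeding.

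**Step 3. Does another text settle it?** In part.
- Section 6.3.2.1.1 requires permanent discontinuation of spartalizumab for any Grade 4 immune-related event, and Section 5.4 lists cytopenias among possible immune-related events. Section 6.3.2 then normally stops the partner drug too, with stated exceptions. The immune-mediated case is therefore settled for spartalizumab.
- Section 6.3.2.2 confines Tables 8-8 and 8-9 to related events without specific requirements elsewhere. This removes the immune-mediated case from the table but does not choose between two lines inside it.
- The life-threatening item in the general lists would cover some Grade 4 platelet events, but a Grade 4 laboratory value is not necessarily life-threatening.
- Section 6.7 lets the investigator stop a drug judged detrimental. That is discretion, and it does not say which mandatory line applies.

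The non-immune case remains open.

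**Step 4. Effect on DLT counting.** Table 7 (Section 6.2.3) lists Grade 4 thrombocytopenia as a DLT in its own right. Whether the drugs are later restarted or stopped, a related event in the first 6 weeks counts once. The DLT count is the same under both rows.

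**Step 5. General lists against the tables.**
- *Recurrent Grade 3.* If recurring means the second event, Section 6.3.2 stops treatment where Table 8-8 (neutropenia) and Table 8-9 restart it. Section 6.3.2 gives no count for recurring. Its general qualifier and its pointer to the tables suggest that the tables govern.
- *Life-threatening.* Section 6.3.2 stops both drugs, while Table 8-9 permits restart after a first Grade 4 event. The two overlap only for Grade 4 events that are life-threatening and not immune-related. Section 9.1.1 pairs the two terms only where CTCAE has no grade. The description of Grade 4 as life-threatening in Table 8.0 belongs to immune-related diarrhea/colitis, which Table 8-9 excludes. Overlap is possible, but its extent cannot be fixed from the text.

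**Step 6. Cross-reference.** The expansion stopping rule in Section 12.1 cites Section 6.3.2 for the DLT definition. The definition and Table 7 are in Section 6.2.3.

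**The case against.** The strongest reply is that the sentence sits in a neutropenia cell, so it may be meant for thrombocytopenia accompanying neutropenia, with the dedicated row governing isolated thrombocytopenia. That reading is available, but nothing in the table states it, and a mandatory rule should not depend on it. The reply is right that immune-mediated Grade 4 events are governed elsewhere, so it would be wrong to infer that every Grade 4 thrombocytopenia is left without a clear rule.

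A reader might also infer that the general lists in Section 6.3.2 flatly contradict Tables 8-8 and 8-9. The documents do not support that. The lists are qualified as general, they point to the tables, and recurring is undefined. The scope sentence in Section 6.3.2.2 also gives some order. What stands is an ambiguity worth one clarifying sentence.

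A reader might further infer that the recommended dose or the expansion halting rule is compromised. For Grade 4 thrombocytopenia it is not, because the DLT is counted either way. For the general lists, a narrow route exists: under Table 7, an event that leads to permanent discontinuation is a DLT, so a second Grade 3 neutropenia within 6 weeks could count under one reading and not the other. The documents give no event rates, so no effect on DLT or halting probabilities can be claimed.

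**Conclusion.** The contradiction in Table 8-8 is real. For a related Grade 4 thrombocytopenia that is not immune-mediated and that recovers to Grade 2 or baseline within 12 weeks, one row allows 0 restarts of both drugs and the other allows up to 2. This rests on the plain words of the two rows and on the absence of any text that ranks them. It is a patient-safety and compliance defect and does not alter DLT counts for that event.

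The gap between the Section 6.3.2 lists and Tables 8-8 and 8-9 is secondary. It depends on how recurring is read and on which Grade 4 events are life-threatening, and the text leans toward the tables for recurrent Grade 3 events.

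**What to change.** 1. **Table 8-8.** Keep one action for Grade 4 thrombocytopenia. The safer default, consistent with the Grade 4 immune-related rule, is to remove Grade 4 from the interrupt-and-restart row and its matching 12-week text. That row then covers only Grade 3 with clinically significant bleeding. Add a separate Grade 4 thrombocytopenia row requiring permanent discontinuation of both drugs. If the clinical team intends restart, delete thrombocytopenia from the sentence in the neutropenia row instead.
2. **Section 6.3.2.** Add one sentence saying that Tables 8-8 and 8-9 govern recurrent Grade 3 related events. Keep the existing order of scope, with the event-specific rules in Section 6.3.3 applied before Tables 8-8 and 8-9. For example, Grade 3 hyperuricemia resumes at a lower siltuximab dose under Section 6.3.3, whereas Table 8-9 would resume at the same dose.
3. **Table 8-9.** Preserve the life-threatening stop by limiting restart after a first Grade 4 event to events that are not life-threatening.
4. **Section 12.1.** Change the DLT reference in the expansion stopping rule from Section 6.3.2 to Section 6.2.3.

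The cost is protocol wording only. Sample size, visits and planned analyses are unchanged.
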